Redness	≥2 Years to <12 years	1 to 4 caliper units (or measuring device units) = 0.5 to 2.0 cm	5 to 14 caliper units (or measuring device units) = >2.0 to 7.0 cm	>14 caliper units (or measuring device units) = >7 cm	Necrosis or exfoliative dermatitis
	≥12 Years	5 to 10 caliper units (or measuring device units) = >2.0 to 5.0 cm	11 to 20 caliper units (or measuring device units) = >5.0 to 10.0 cm	>20 caliper units (or measuring device units) = >10 cm	Necrosis or exfoliative dermatitis
Swelling	≥2 Years to <12 years	1 to 4 caliper units (or measuring device units) = 0.5 to 2.0 cm	5 to 14 caliper units (or measuring device units) = >2.0 to 7.0 cm	>14 caliper units (or measuring device units) = >7 cm	Necrosis
	≥12 Years	5 to 10 caliper units (measuring device units) = >2.0 cm to 5.0 cm	11 to 20 caliper units (measuring device units) = >5.0 cm to 10.0 cm	>20 caliper units (or measuring device units) =>10 cm	Necrosis

Table 2. Local Reaction Grading Scale

- a. Parent(s)/legal guardians of participants <12 years of age experiencing local reactions >14 caliper units (>7 cm), participants or parent(s)/legal guardians of participants ≥12 years of age experiencing local reactions >20 caliper units (>10 cm), and parent(s)/legal guardians of participants experiencing Grade 3 pain at the injection site are to be contacted by the study site. An unscheduled visit may be required.
- b. Only an investigator or qualified designee is able to classify a participant's local reaction as Grade 4, after clinical evaluation of the participant or documentation from another medically qualified source (eg, emergency room or hospital record). Grade 4 local reactions will be collected on the AE CRF and assessed by the investigator using the AE intensity grading scale as detailed in Section 10.2.3.

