8.3.4.3. Systemic Events

During the reactogenicity e-diary reporting period, participants or participants' parent(s)/legal guardians will be asked to assess vomiting, diarrhea, headache, fatigue/tiredness, muscle pain, and joint pain and to record the symptoms in the reactogenicity e-diary. The symptoms will be assessed by the participant or participant's parent(s)/legal guardian as absent, mild, moderate, or severe according to the grading scale in Table 3.

If a Grade 3 systemic event is reported in the reactogenicity e-diary, a telephone contact should occur to ascertain further details and determine whether a site visit is clinically indicated. Only an investigator or medically qualified person is able to classify a participant's systemic event as Grade 4. If a participant experiences a confirmed Grade 4 systemic event, the investigator must immediately notify the sponsor and, if it is determined to be related to the administration of the study intervention, further vaccinations (if applicable) will be discontinued in that participant.

Table 3. Systemic Event Grading Scale for Participants ≥2 Years of Age

	Mild (Grade 1)	Moderate (Grade 2)	Severe (Grade 3)	Potentially Life-Threatening (Grade 4) ^a
Vomiting	1-2 times in 24 hours	>2 times in 24 hours	Requires IV hydration	Emergency room visit or hospitalization for severe vomiting
Diarrhea	2 to 3 loose stools in 24 hours	4 to 5 loose stools in 24 hours	6 or more loose stools in 24 hours	Emergency room visit or hospitalization for severe diarrhea
Headache	Does not interfere with activity	Some interference with activity	Prevents daily routine activity	Emergency room visit or hospitalization for severe headache
Fatigue/tiredness	Does not interfere with activity	Some interference with activity	Prevents daily routine activity	Emergency room visit or hospitalization for severe fatigue/tiredness
Muscle pain	Does not interfere with activity	Some interference with activity	Prevents daily routine activity	Emergency room visit or hospitalization for severe muscle pain
Joint pain	Does not interfere with activity	Some interference with activity	Prevents daily routine activity	Emergency room visit or hospitalization for severe joint pain

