a. Only an investigator or qualified designee is able to classify a participant's systemic event as Grade 4, after clinical evaluation of the participant or documentation from another medically qualified source (eg, emergency room or hospital record). Grade 4 local reactions will be collected on the AE CRF and assessed by the investigator using the AE intensity grading scale as detailed in Section 10.2.3.

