- When an AE or SAE occurs, it is the responsibility of the investigator to review all documentation (eg, hospital progress notes, laboratory reports, and diagnostic reports) related to the event.
- The investigator will then record all relevant AE or SAE information in the CRF.
- It is **not** acceptable for the investigator to send photocopies of the participant's medical records to Pfizer Safety in lieu of completion of the Vaccine SAE Reporting Form/AE or SAE CRF page.
- There may be instances when copies of medical records for certain cases are requested by Pfizer Safety. In this case, all participant identifiers, with the exception of the participant number, will be redacted on the copies of the medical records before submission to Pfizer Safety.

• The investigator will attempt to establish a diagnosis of the event based on signs, symptoms, and/or other clinical information. Whenever possible, the diagnosis (not the individual signs/symptoms) will be documented as the AE or SAE.

Assessment of Intensity

The investigator will make an assessment of intensity for each AE and SAE reported during the study and assign it to 1 of the following categories:

GRADE	If required on the AE page of the CRF, the investigator will use the adjectives MILD, MODERATE, SEVERE, or LIFE-THREATENING to describe the maximum intensity of the AE. For purposes of consistency, these intensity grades are defined as follows:	
1	MILD	Does not interfere with participant's usual function.
2	MODERATE	Interferes to some extent with participant's usual function.
3	SEVERE	Interferes significantly with participant's usual function.
4	LIFE-THREATENING	Life-threatening consequences; urgent intervention indicated.

An event is defined as "serious" when it meets at least 1 of the predefined outcomes as described in the definition of an SAE, NOT when it is rated as severe.

Assessment of Causality

- The investigator is obligated to assess the relationship between study intervention and each occurrence of each AE or SAE. The investigator will use clinical judgment to determine the relationship.
- A "reasonable possibility" of a relationship conveys that there are facts, evidence, and/or arguments to suggest a causal relationship, rather than a relationship cannot be ruled out.

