## 3.1.1.1.2. Maximum Severity of Local Reactions Within 7 Days After Vaccination

The grading of local reactions is listed in Table 4.

**Table 4.** Grading Scale for Local Reactions

	Mild Grade 1	Moderate Grade 2	Severe Grade 3	Grade 4 a
Redness	Mild grading from the e-diary per Table 2 in the protocol or mild from the AE CRF	Moderate grading from the e-diary per Table 2 in the protocol or moderate from the AE CRF	Severe grading from the e-diary per Table 2 in the protocol or severe from the AE CRF	Necrosis or exfoliative dermatitis
Swelling	Mild grading from the e-diary per Table 2 in the protocol or mild from the AE CRF	Moderate grading from the e-diary per Table 2 in the protocol or moderate from the AE CRF	Severe grading from the e-diary per Table 2 in the protocol or severe from the AE CRF	Necrosis

	Mild Grade 1	Moderate Grade 2	Severe Grade 3	Grade 4ª
Pain (at the injection site)	Does not interfere with activity (mild from the e-diary or AE CRF)	Interferes with activity (moderate from the e-diary or AE CRF)		Emergency room visit or hospitalization for severe pain at the injection site

**Table 4.** Grading Scale for Local Reactions

The following variables are derived for each participant:

1. Maximum severity of each local reaction on any day (Day 1 through Day 7).

The maximum severity (highest grading) of each local reaction within 7 days after vaccination will be derived. The maximum severity will be derived as follows:

- = Missing, if values are missing for all days (Days 1-7);
- = 0, if the participant reports all reactions as "no" or a combination of missing and "no" for all days (Days 1-7);
- = Highest grade (maximum severity either from the e-diary or in the AE CRF) within 7 days after vaccination if the answer is not "no" for at least 1 day.
- 2. Maximum severity of any local reaction on any day (Day 1 through Day 7).

The maximum severity for any local reaction will be derived as follows:

- = Missing, if values are missing for all days (Days 1-7) across all 3 local reactions;
- = 0, if the participant reports all reactions as "no" or a combination of missing and "no" for all days (Days 1-7) for all individual local reactions;
- = *Highest grade* (maximum severity) within 7 days after vaccination, if the answer is not "no" for at least 1 day for at least 1 local reaction.

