#### 3.1.1.3. Duration of Each Local Reaction

The duration of each local reaction will be calculated in days as the resolution date of reaction - start date of reaction + 1. Resolution of the event is the last day on which the event is recorded in the e-diary (or AE CRF) or the date the event ends if it is unresolved during the participant e-diary recording period (end date collected on the CRF) or AE stop date, whichever is longer, unless chronicity is established.

If there is no known end date, the duration will be considered unknown and set to "missing". Participants with no reported reaction have no duration.

Grade 4 assessment should be made by the investigator using the AE severity grading scale. The assessment will be collected on the AE CRF and thus not reported from the e-diary.

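### Outside fever, a prompted event that meets the protocol's Grade 4 criterion but is rated severe on the AE CRF can be tabulated as Grade 3

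*SAP*

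**What the plan says.** **Local reactions.** SAP 3.1.1.1.2 refers to Table 4 for grading. The Grade 4 cells are "Emergency room visit or hospitalization for severe pain at the injection site" for pain, "Necrosis or exfoliative dermatitis" for redness, and necrosis for swelling. Protocol Table 2 has the same criteria. The note to the Grade 4 column (in the text as read it falls under the duration heading that follows) states: "Grade 4 assessment should be made by the investigator using the AE severity grading scale". It adds that this assessment comes through the AE CRF and not the e-diary. Maximum severity is then the highest grade, described as "maximum severity either from the e-diary or in the AE CRF".

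**The AE scale.** In Protocol 10.2.3, Grade 3 is severe, meaning significant interference with usual function. Grade 4 is "Life-threatening consequences; urgent intervention indicated".

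**Systemic events.** Protocol Table 3 makes an emergency-room visit or hospitalisation the Grade 4 criterion for each of the six non-fever events, for example "Emergency room visit or hospitalization for severe headache". SAP 3.1.1.2 refers to the protocol for the scale. It then derives daily severity as the maximum of the e-diary and AE CRF ratings, and says that systemic events are handled in the same manner as local reactions. The footnote to Table 3 reads "Grade 4 local reactions will be collected on the AE CRF and assessed by the investigator using the AE intensity grading scale", a sentence that belongs under Table 2.

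**Fever.** SAP 3.1.1.2 raises a fever rated severe on the AE CRF to Grade 4 if a temperature above 40.0°C is documented through a query or another source.

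**The concern.** An emergency-room visit and a life-threatening event are different things. A child taken to the emergency room for severe injection-site pain or headache and then sent home meets the Table 2 or Table 3 criterion, yet an investigator could properly rate the AE as severe and not life-threatening. If the tabulated grade follows the AE rating, the event is shown one grade too low.

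This matters because maximum severity is part of the primary safety display (Protocol Table 5; SAP 6.1.1.1), and a Grade 4 count in a small paediatric dose-finding group is a figure that readers look for. The main AE variables would not show the event either, because SAP 3.1.1.3 (Adverse Events and Serious Adverse Events) removes non-serious reactogenicity from them.

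**Working it through.** The documents give no figure on this point to reproduce. The check is a trace of the grading rules, followed by the effect of one child on a table row.

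**Step 1: which events.** There are 3 local reactions and 7 systemic events, 10 in all. Fever has its own rule, which leaves 10 − 1 = 9. For 3 of these (local) the mismatch is explicit in the SAP. For the other 6 (systemic) the gap lies in the derivation only.

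**Step 2: trace for an event that meets the criterion.** The e-diary can supply at most severe (Grade 3), because only an investigator or other medically qualified person may assign Grade 4. In SAP Table 4, severe on the AE CRF falls under Grade 3 in the redness and swelling rows; the pain cell is not legible in the text as read. Reading the AE CRF on its own scale, as the Table 4 note directs, the tabulated grade is max(e-diary, AE CRF):

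| AE CRF rating | Tabulated grade (e-diary severe) | Grade by Table 2/3 criterion |
|---|---|---|
| Mild | max(3, 1) = 3 | 4 |
| Moderate | max(3, 2) = 3 | 4 |
| Severe | max(3, 3) = 3 | 4 |
| Life-threatening | max(3, 4) = 4 | 4 |

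Taking the higher of the two sources, as SAP 3.1.1 also says, does not help when neither exceeds Grade 3. This trace rests on the note. If the Table 4 cells alone governed, a local reaction meeting the criterion would be Grade 4 whatever its AE rating.

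**Step 3: other sources and outputs.**
- At an unscheduled visit the site grades pain and systemic events by Tables 2 and 3 and completes a dedicated CRF page (Protocol 8.11), but the SAP severity derivation does not name that page as a source.
- The reactogenicity sensitivity analysis (SAP 6.1.1.3) uses e-diary data only, so it cannot recover the grade.
- The AE sensitivity analysis (SAP 6.1.2.3) keeps the event, at its AE CRF intensity of severe.
- Admission to a hospital or emergency ward counts as hospitalisation (Protocol 10.2.2), so an admitted child is an SAE and stays in the AE tables.

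The exposed case is therefore mainly an emergency-room visit without admission that is judged non-serious.

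**Step 4: effect of one child.** Clopper-Pearson limits are the 0.025 quantile of Beta(x, n − x + 1) and the 0.975 quantile of Beta(x + 1, n − x). For x = 0 the lower limit is 0 and the upper limit is 1 − 0.025^(1/n). Group sizes are about 20 for an age/risk/dose group in the SAP and about 40 for the older stratum at one dose level.

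| Group | Grade 4 by criterion | Grade 4 if misgraded |
|---|---|---|
| n = 20 | 1/20 = 5.0% (0.13 to 24.87%) | 0/20 = 0% (0 to 16.84%) |
| n = 40 | 1/40 = 2.5% (0.06 to 13.16%) | 0/40 = 0% (0 to 8.81%) |

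The Grade 3 row gains the same child, so the any-severity and Grade 3-or-higher counts change by 0.

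**The case against.** The protocol footnotes can be read as two steps: first classify Grade 4 from clinical evaluation or an emergency-room or hospital record, then give the event an AE intensity as well. On that reading AE intensity never decides the grade. SAP Table 4 lends support: its redness and swelling cells for Grades 1 to 3 each add an AE CRF mapping, while the Grade 4 cells give only the clinical criterion. This stands as a reasonable reading and shows that a correct result is possible. It does not settle the matter, because the SAP note makes the AE scale the means of Grade 4 assessment and no rule says which prevails.

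Safeguards exist. The investigator must notify the sponsor at once of a confirmed Grade 4 reaction or event (Protocol 8.3.4.2 and 8.3.4.3). Protocol 8.11 requires contact to check a suspected Grade 4 against the tables, and the clinical team reviews AEs from the first 7 days before database lock (SAP 3.1.1). These steps make an unnoticed case unlikely, but none of them changes the written derivation. The AE CRF layout and the sponsor's severity rules are not in the documents, so an existing mapping cannot be ruled out.

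A reader might infer that all nine events carry two conflicting Grade 4 definitions. The documents do not support that for the systemic events: SAP 3.1.1.2 defers to the protocol scale, and the Table 3 footnote's reference to local reactions is evidently a copying error.

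**Conclusion.** The point holds in limited form. For local reactions, the SAP Table 4 cells and their note disagree on what makes a Grade 4. For the six non-fever systemic events, the derivation gives the Table 3 criterion no route into the tabulated grade. In either case an event confirmed as meeting the criterion but rated severe on the AE CRF can be shown as Grade 3.

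The effect is confined to the split between Grades 3 and 4: one child, or 5.0 percentage points in a group of 20 and 2.5 in a group of 40. The documents give neither the rate of such emergency-room visits nor how investigators would rate them, so no probability of misgrading is claimed.

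A reader might also infer that the stopping rules are compromised. They are applied through ongoing review of events and not through this derivation (Protocol 8.3.5). Rule 2 does depend on Grade 4 as set out in Section 8.3.4, which is a reason to make the footnotes there unambiguous.

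Priority is minor. Confidence is medium for the local reactions and lower for the systemic events.

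**What to change.** **SAP.** In the Table 4 note and in Section 3.1.1.2, state that Grade 4 is assigned when the investigator has confirmed the Protocol Table 2 or Table 3 criterion, whatever the AE CRF intensity. Accept confirmation by CRF query, data handling memo or the unscheduled visit page, on the model of the existing fever rule. Report AE intensity separately.

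**Protocol.** In the footnotes to Tables 2 and 3, state that AE intensity does not replace the Grade 4 classification. This also keeps stopping rule 2 clear. Under Table 3, change 'local reactions' to 'systemic events'.

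**Cost.** Wording in two SAP places and two protocol footnotes, plus a few queries for prompted events that involved an emergency-room visit. Where an unscheduled visit took place, the grades for pain and systemic events are already assessed. Sample size and visits do not change. The SAP change should be in place before database lock.

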## 3.1.1.4. Onset Day of Each Local Reaction

The onset day of each local reaction will be derived. Onset day is defined as the first day of reporting any severity.

For the onset day of each local reaction, if the participant reports changes in severity of the local reaction, only the first day of reporting that specific local reaction will be counted.

## 3.1.1.1.5. Presence of Each and Any Local Reaction on Each Day and Any Day

Presence (yes or no) of each and any local reaction on each of the 7 days (Day 1 through Day 7) follows the derivation as described in Table 5.

Table 5. Derived Variables for Each and Any Local Reaction on Each Day and Any Day

Variable	Yes (1)	No (0)	Missing (.)
Each local reaction on a specific day	The participant reports the reaction on a specific day for a specific local reaction.	The participant reports the reaction as "no" on that specific day.	The participant reports the specific local reaction as missing on that specific day.
Any local reaction on a specific day	The participant reports the reaction on a specific day for any of the 3 local reactions.	The participant reports the reactions as "no" or a combination of "no" or missing on that specific day across all 3 local reactions.	The participant reports all 3 local reactions as missing on that specific day.
Each local reaction on any day	The participant reports that local reaction on any day (Days 1-7).	The participant reports the local reaction as "no" or a combination of "no" and missing across all 7 days.	The participant reports the local reaction as missing on all 7 days.
Any local reaction on any day	The participant reports any local reaction on any day (Days 1-7).	The participant reports the reactions as "no" or missing across all 7 days and across all 3 local reactions.	The participant reports all 3 local reactions as missing on all 7 days.

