# 3. ENDPOINTS AND BASELINE VARIABLES: DEFINITIONS AND CONVENTIONS

## 3.1. Primary Endpoint(s)

#### 3.1.1. Primary Safety Endpoints

Primary safety endpoints include both reactogenicity data collected from the e-diary and AE data collected from the CRF.

Based on feedback from the FDA on multiple vaccine programs, reactogenicity data will utilize both e-diary data (prompted local reactions and systemic events) and reactogenicity events (related or unrelated) reported in the AE CRF during the e-diary collection period. Since the AE CRF does not designate a specific page to collect reactogenicity data for an untransmitted e-diary, Pfizer has adopted a process of providing a listing of AEs reported within 7 days after vaccination to the clinical team to review and determine ("flag") which

PTs should be considered reactogenicity events before the database lock. AEs reported on the same day of vaccination but missing a start time are defaulted to AEs reported after vaccination. Following these review steps, those AEs reported within 7 days after vaccination that match flagged PTs (either related or unrelated) will be considered reactogenicity data. If the same reactogenicity event is reported on the same day from both the e-diary and the AE CRF, the highest grade from the 2 data sources will be used for that specific day for analysis.

It should be noted that the data collection in the AE CRF is different from that of the e-diary:

- For redness, swelling, and fever, the measured size of redness and swelling at the injection site and temperature are recorded in the e-diary, but not in the AE CRF. As the missing e-diary entries are monitored with ongoing review of the prompted reactions reported in the AE CRF, any measurement recorded in the query response will be taken into consideration for the primary analysis using the data handling memo for analysis purposes. For the 7 days, only the maximum grading from both sources will be used for the aggregated severity analysis.
- For pain at the injection site and all other systemic events, the severity grading algorithm for the e-diary data and the AE CRF may not be the same. Pfizer will choose the highest-severity grade.

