## 3.1.1.1. Local Reactions Within 7 Days After Vaccination

The local reactions include redness, swelling, and pain at the injection site from Day 1 through Day 7 after vaccination, where Day 1 is the day of vaccination with RSVpreF. Any reported reactogenicity events in the AE CRF during the e-diary collection period are included in the derivation discussed below.

The following section describes derivations with details for the assessment of local reactions: any presence, maximum severity, duration, and onset day of local reactions, in addition to presence of local reactions on each day, for each vaccine group as mentioned above.

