## 3.4.3. E-Diary Completion

An e-diary will be considered transmitted if any data for the local reactions and systemic events are present for any day. If all data are missing for all items (local reactions and systemic events) on the e-diary for all 7 days after vaccination, then the e-diary will be considered not transmitted. An e-diary will be considered transmitted for a given day if any data are present for that day.

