#### 5.3.1.1. Reactogenicity Data

For derived variables based on the reactogenicity data, if any day of the 7-day e-diary is available, the "any day (Days 1-7)" data will be considered nonmissing.

The reactogenicity data are collected in the e-diary, which does not allow participants to skip any questions. Therefore, for a specific day, if the e-diary data are transferred for that day, all of the reactogenicity data for the participant on that day are nonmissing. In general, for any participant with all 7 days of the e-diary data missing, this participant will not be included in the analysis (ie, assuming MCAR). If only 1 through 6 days of e-diary data are transferred, it is expected that any missed reactogenicity events would be entered in the AE CRF if any experienced reactogenicity was not reported in the e-diary due to missed days. Therefore, the primary analysis will use reactogenicity recorded in the AE CRF to impute the partially missed e-diary data to estimate the reactogenicity rate during the e-diary collection period. The AE CRF is designed as a log page, which means only events that occurred will be recorded and events that did not occur will not be recorded. Therefore, all remaining missing days are considered as "no." This imputation can reasonably estimate the reactogenicity event rates during the e-diary collection period.

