## 6.1.1.2. Supplementary Analysis

To support the assessment of reactogenicity, the endpoints below, as specified in Section 3.1.1.1 and Section 3.1.1.2, will be summarized per the supplemental analysis with the same analysis population:

- Duration (days) of each local reaction and each systemic event after vaccination.
- Onset day of each local reaction and each systemic event after vaccination.
- Presence of each and any local reaction and each and any systemic event, on each of the 7 days and for "any day (Days 1-7)."

The presentation of the results will include a basic descriptive summary without the 95% CIs for each group.

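### For the by-day reactogenicity summary, SAP Table 5 and SAP 5.3.1.1 code an event-free unsent diary day differently; taken literally, Table 5 counts unsent days only when they carry an event

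*SAP*

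**What the plan says.** SAP 6.1.1.2 lists, among the supplementary outputs, "Presence of each and any local reaction and each and any systemic event, on each of the 7 days". It uses the same population as the main analysis, that is, children with at least 1 transmitted diary day, and presents descriptive results without confidence intervals.

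SAP 3.1.1.1 puts AE CRF events into the local-reaction derivations: "Any reported reactogenicity events in the AE CRF during the e-diary collection period are included in the derivation discussed below". The derivations it then names include presence by day ("in addition to presence of local reactions on each day, for each vaccine group as mentioned above"). SAP 3.1.1 merges the two sources at day level: "If the same reactogenicity event is reported on the same day from both the e-diary and the AE CRF, the highest grade" of the two is used.

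Table 5 in SAP 3.1.1.1.5 defines the coding. For one reaction on a specific day, *no* requires a reported *no* on that day, and *missing* is a separate category: "The participant reports the specific local reaction as missing on that specific day". The row for any local reaction on a specific day is *missing* when all 3 reactions are missing. The any-day rows of the same table fold missing days into *no*.

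SAP 5.3.1.1 says the diary does not allow questions to be skipped, so an unsent day is missing for every item. When 1 to 6 days are sent, it expects missed events to be in the AE CRF, and then: "Therefore, all remaining missing days are considered as" *no*. SAP 3.1.1.2 handles systemic events in the same way as local reactions.

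**The concern.** Take a child who sent some diaries but not the one for a given day. If the AE CRF holds a flagged event for that day, the child is a *yes*. If it does not, the child is *missing* under Table 5 and *no* under 5.3.1.1. Two programmers could each follow the SAP and produce different numbers for the same cell.

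The literal Table 5 reading has a further defect. If missing days leave the denominator, an unsent day enters the calculation only when it carries an event. Denominators can also differ between reactions on one day: an AE CRF report of pain keeps that child in the pain row but leaves redness and swelling *missing*.

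The by-day summary shows when reactions peak and how fast they clear in each age, risk and dose group. With about 20 children per group, a few unsent diaries can change a daily percentage visibly. The e-diary-only sensitivity analysis in SAP 6.1.1.3 covers maximum severity only, so it would not expose the problem.

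**Working it through.** The documents give no daily percentage or diary compliance figure, so there is nothing to reproduce. The check is algebra over assumed values.

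**Inputs.** N is the number of children with at least 1 diary day, about 20 per group (SAP 2.3). The rest are assumptions: m, diaries unsent that day; s = (N − m)/N, the share sent; p, event rate on sent days; q, event rate on unsent days; c, the share of unsent-day events that reach the AE CRF. SAP 5.3.1.1 expects missed events to be entered, which corresponds to c = 1.

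**Formulas.**
- Table 5 taken literally, missing days dropped: [(N − m)p + mqc] / [(N − m) + mqc]
- SAP 5.3.1.1: [(N − m)p + mqc] / N
- True rate: [(N − m)p + mq] / N

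The first two share a numerator. The Table 5 denominator is smaller by the number of unsent days without an AE CRF event, so its percentage is never lower than that of 5.3.1.1. At c = 1 the 5.3.1.1 result equals the true rate, so Table 5 cannot fall below it.

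**Full capture, same rate on sent and unsent days (c = 1, q = p).** Table 5 reduces to p / [s + (1 − s)p].

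| Share sent | p = 10% | p = 30% |
|---|---|---|
| 95% | 0.10/0.955 = 10.5% | 0.30/0.965 = 31.1% |
| 90% | 0.10/0.91 = 11.0% | 0.30/0.93 = 32.3% |
| 80% | 0.10/0.82 = 12.2% | 0.30/0.86 = 34.9% |
| 70% | 0.10/0.73 = 13.7% | 0.30/0.79 = 38.0% |

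**Incomplete capture (s = 80%, p = q = 10%).**
- c = 0.5: Table 5 gives 0.09/0.81 = 11.1%; 5.3.1.1 gives 9.0%.
- c = 0: Table 5 gives 0.08/0.80 = 10.0%, which is correct; 5.3.1.1 gives 8.0%.

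**Incomplete capture with more events on unsent days** (N = 20, m = 4, p = 20%, q = 50%, c = 0.5). The numerator is 3.2 + 1.0 = 4.2. Table 5 gives 4.2/17 = 24.7%, and the true rate is (3.2 + 2.0)/20 = 26.0%. Here Table 5 is too low.

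**In counts.** Of 20 children, 4 diaries are unsent that day, with 3 diary *yes* and 1 AE CRF *yes*. Table 5 gives 4/17 = 23.5%, 5.3.1.1 gives 4/20 = 20.0%, and sent diaries alone give 3/16 = 18.8%.

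**Coherence.** Suppose all reactions fall on Day 1: 4 *yes* among 16 sent diaries and 2 AE CRF events among 4 unsent. Table 5 gives 6/18 = 33.3% for Day 1, while the any-day rate is 6/20 = 30.0%. A single-day rate should not exceed the any-day rate in the same children.

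**The case against.** The strongest reply is that 5.3.1.1 is already a day-level rule. If it is applied before Table 5, the conflict disappears, and the SAP never says that missing days leave the by-day denominator. On this view the *missing* column only lists generic data states. The any-day rows also have a *missing* category that cannot apply to anyone in the analysis set, and Table 5 allows a mix of *no* and missing across reactions on one day, which a diary without skipping cannot produce.

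This stands as a plausible account of the intention, but it does not settle the text. SAP 5.3.1 sends the reader to the endpoint sections for missing-data rules, which favours Table 5. SAP 5.3.1.1 ties its imputation to the primary analysis, whereas the by-day summary is supplementary. If the sponsor meant the by-day summary to differ for that reason, the asymmetry remains.

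It is also fair that the effect may be small. Protocol 8.10.1 calls daily diary review optimal, Protocol 8.12 requires contact with families who are not completing the diary, and SAP 6.5.2 summarizes diary completion. At 80% sent and 10% prevalence the excess is 2.2 points, less than one child in 20 (5 points).

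A reader might infer that the daily percentages will certainly be biased upward, or that the dose decision is compromised. The documents support neither. The bias depends on how Table 5 is programmed and on AE CRF capture, and nothing ties the internal review committee's decisions to this table.

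**Conclusion.** The conflict between the specific-day rows of Table 5 and SAP 5.3.1.1 is real. If Table 5 is programmed literally with missing days dropped, and missed events reach the AE CRF as the SAP expects, daily percentages are too high whenever there are event-free unsent days and at least one event. With equal event rates on sent and unsent days, a 10% rate would show as about 10.5% at 95% sent, 12.2% at 80% and 13.7% at 70%. These shares and rates are assumptions. With incomplete capture the direction is not certain.

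The reach is limited to the supplementary by-day summaries of local reactions and, by reference, systemic events. The primary any-day and maximum-severity results already count missing days as *no* and do not change. The point is worth correcting because the SAP gives two answers for one cell, one of which can produce an incoherent table.

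**What to change.** In the specific-day rows of Table 5, and for the parallel systemic-event variables in SAP 3.1.1.2, state that for a child with at least 1 transmitted diary day, an unsent day without a flagged AE CRF event is *no*. In other words, 5.3.1.1 is applied before Table 5. N for every day is then all children with at least 1 transmitted day, and single-day and any-day rates share a denominator.

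Beside each day, print the number of diaries transmitted that day. SAP 3.4.3 already supplies the definition: "An e-diary will be considered transmitted for a given day if any data are present for that day".

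Optionally, add an e-diary-only by-day display with N equal to the diaries transmitted that day, as a sensitivity display. It should not replace the main table. It would drop AE CRF-only events, against the two-source approach of SAP 3.1.1, and could leave a child *yes* for any day but on no single day.

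The cost is a few lines of SAP text and one extra count per day. The downside is that daily rates will be low if AE CRF backfill is incomplete (8.0% against 10% in the worst case above, at 80% sent with no capture). The printed transmitted count lets a reader see where that could matter.
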